This study is a Phase 3 multicenter study in subjects with acute migraine. The study is designed to evaluate the safety and tolerability of long-term intermittent use of lasmiditan 200 mg and lasmiditan 100 mg given as a first dose for the treatment of a migraine attack. A second dose of study drug is allowed to investigate the safety of lasmiditan 200 mg and lasmiditan 100 mg when taken for rescue or when taken for recurrence of migraine. In addition to safety assessments, the efficacy of long term intermittent use of lasmiditan will be evaluated. Data from this study will be used to further investigate and confirm the safety and efficacy of

lasmiditan in the treatment of acute migraine in patients with risk factors for cardiovascular disease.

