10.2 Randomization

This is a multicenter, randomized, open-label, parallel group study.

Subjects will be centrally randomized to one of two treatments to receive lasmiditan 200 mg (L200 mg) or lasmiditan 100 mg (L100 mg) in a 1:1 ratio. Subjects will be stratified (yes or no) for use of concomitant medications that reduce the frequency of migraine episodes. Subject will be randomized and study drug will be dispensed at each study visit.

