#### 4.1 Examination of Subgroups

Subgroup analyses will be performed for subjects with one or more cardiovascular risk factors. Similar criteria as parent study will be used to identify the subjects with one or more cardiovascular risk factors. It should be noted that the parent or current study was not designed to detect treatment differences with high statistical power within subgroups.

- Cardiovascular Disease Risk Factors
  - Hypertension
  - Hypercholesterolemia
  - Smoking
  - Obesity
  - Diabetes Mellitus
  - Strong family history of coronary artery disease
  - Males over 40 years
  - Post-menopausal females

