### **5.1 Changes and Clarifications from the Planned Analysis**

The protocol detailed mITT-2nd Dose and PP-2nd Dose populations. However, the decision was made to run efficacy analyses on the ITT and mITT populations. The populations such as safety-2nd, mITT-2nd Dose and PP-2nd Dose populations were therefore removed. Additionally PP population was removed, as primary endpoint of this study is safety.

The analyses of the primary efficacy measure and other related measures described in the protocol were limited to headaches that were of moderate or severe intensity at the time of dosing. In keeping with subsequent input to CoLucid from the Food & Drug Administration (FDA), the efficacy endpoints will take into account headaches that were of mild intensity at the time of treatment.

The protocol mentioned sensitivity analysis for efficacy endpoints for missing diary data. It was decided not to conduct this analysis, as primary endpoint of this study is safety. The complications of missing efficacy diary data were tested in parent study.

The protocol does not mention an additional subgroup analysis but subgroup analyses described in Section 11.8 will be provided.

Though the protocol did not specify this, it was decided that exploratory analyses would be repeated separately for relief of each associated symptom of headache, including vomiting.

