- Subgroup analysis will be presented for subject with cardiovascular risk factors. TEAE will be compared among subjects with and without CVRF for individual event for Safety population. They will be tested with chi-squared test or fisher's exact test as appropriate with respect to sample size and all comparisons will be done at level of significance of 0.05.

Above tables will be presented for various types of AE criteria as below:

1. Incidence of TEAE table will be provided by-subject analysis. For this analysis, the adverse events will be reported out of total number of subjects in each treatment group regardless of whether a second dose is taken.
2. Similar events as Point #1 will be reported when only 1 dose was taken and additionally when 2 doses were taken.

3. Incidence of serious adverse events table will be reported by-subject analysis for each treatment group regardless of whether a second dose is taken.
4. Similarly, to Point # 2, serious events will be reported when only 1 dose was taken and additionally when 2 doses were taken.
5. TEAEs summary will be provided by each treated migraine analysis. For this analysis, the adverse events will be reported out of total number of treated migraines for each treatment group regardless of second dose.
6. Additionally TEAE by-subject analysis will be provided for treated 1st migraine attack, 2nd migraine attack, 3rd migraine attack, 4th migraine attack, 5th migraine attack, 10th migraine attack, 15th migraine attack, 20th migraine attack
7. Specific most common TEAEs will be reported in descriptive statistics (n, mean, median, SD, Minimum and maximum) by proportion of treated migraines attacks in subjects experiencing the TEAE at least once. This data will be presented out of total number of subjects in each treatment group. TEAEs will be reported if 2% or more of subjects any any treatment group report the event.

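### The cardiovascular-risk safety comparison in SAP 12.1 rests on unadjusted 0.05 tests of each adverse event between non-randomised groups, without intervals, exposure handling or a list of terms

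*SAP*

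**What the plan says.** SAP 12.1 states: "TEAE will be compared among subjects with and without CVRF for individual event for Safety population". The choice between a chi-squared and a Fisher's exact test depends on the numbers available. The level is fixed for every term: "all comparisons will be done at level of significance of 0.05". Sidedness, the MedDRA level, a frequency cut-off for testing and the number of terms are not stated.

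On the groups, SAP 4.1 says: "Similar criteria as parent study will be used to identify the subjects with one or more cardiovascular risk factors". Its list includes males over 40 and post-menopausal females, besides hypertension, hypercholesterolemia, smoking, obesity, diabetes and family history. The same section adds a caveat on both studies, that each "was not designed to detect treatment differences with high statistical power within subgroups".

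Only dose is randomised: Protocol 10.2 allocates subjects "to one of two treatments to receive lasmiditan 200 mg (L200 mg) or lasmiditan 100 mg (L100 mg) in a 1:1 ratio". Its one stratification factor is use of medication that reduces migraine frequency.

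On purpose, the Protocol introduction (Section 4) says: "Data from this study will be used to further investigate and confirm the safety and efficacy of" the drug in migraine patients who have cardiovascular risk factors. On subgroups in general, SAP 5.1 says that "subgroup analyses described in Section 11.8 will be provided". Section 11 of the SAP has only 11.1 and 11.2, and neither splits a result by CVRF.

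**The concern.** Everything else in the safety and efficacy sections is descriptive. The one place where the SAP calls for p-values is a comparison that randomisation does not protect, in a patient group that the Protocol introduction singles out. Three things can go wrong.

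- **Chance signals.** Testing every term at 0.05 produces some small p-values among common events even when nothing differs.
- **Uninformative negatives.** For rare events, which include the cardiovascular events of most interest, a non-significant test is the likely result whether or not risk is raised. It could be read as reassurance.
- **Differences that are not drug effects.** The groups differ in age and sex by definition, and there is no untreated control. SAP 12.1 counts a subject once per preferred term over up to 12 months, so crude incidence also rises with the number of attacks treated.

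TEAEs are confined to 48 hours after a dose, so a later cardiovascular event falls outside the comparison. On efficacy, the Protocol introduction mentions these patients, but no CVRF efficacy summary is specified anywhere in the SAP.

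**Working it through.** The documents give no power, error-rate or sample-size figure for this comparison, so there is nothing to reproduce.

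**Inputs from the documents.** Alpha is 0.05 per comparison (SAP 12.1). N is about 2580 (Protocol synopsis), used here as an upper bound for the safety population.

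**Assumptions.** Tests are two-sided. Between 20 and 30 terms are tested, independently. The CVRF share is 50% (1290 v 1290) or 80% (2064 v 516). Event rates are as shown below.

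**1. Chance signals, all nulls true.** P(at least one) = 1 − 0.95^K, and the expected number is 0.05K.
- K = 20: 1 − 0.95^20 = 64%, with 1.0 expected.
- K = 30: 1 − 0.95^30 = 79%, with 1.5 expected.

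Fisher's test is conservative. For events at 2% to 10% its actual size at N = 2580 is about 3.6% to 4.6%. That gives 1 − 0.964^20 = 52% to 1 − 0.954^20 = 61% for 20 terms, and 67% to 76% for 30. At an incidence of 0.1% the size is 0.1% to 1.7%, so false signals come mainly from common events.

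**2. Power of the two-sided Fisher test, by exact enumeration of both binomials.**

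| With CVRF v without | 50:50 | 80:20 |
|---|---|---|
| 0.2% v 0.1% | 1.5% | 0.3% |
| 0.3% v 0.1% | 7% | 0.1% |
| 1.0% v 0.5% | 24% | 12% |

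If no event occurs in subjects without CVRF, significance needs at least 6 events in the CVRF group at 50:50, or 17 at 80:20. For 80% power, 0.2% v 0.1% needs about 23,500 subjects per group.

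**3. Unequal exposure (hypothetical).** Suppose the per-attack risk is 2% in both groups, but CVRF subjects treat 9 attacks and the others 6.
- With CVRF: 1 − 0.98^9 = 16.6%, or 343 of 2064.
- Without CVRF: 1 − 0.98^6 = 11.4%, or 59 of 516.
- Pearson chi-squared = 8.43, p about 0.004. Fisher's p is 0.003.

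The planned test declares a difference although the risk per attack is the same.

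**4. What an upper bound would show instead.** With zero events, the exact two-sided 95% upper limit is 1 − 0.025^(1/n): 0.29% for n = 1290 and 0.18% for n = 2064. A p-value carries no such information.

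**The case against.** The strongest reply is that this comparison is exploratory in all but name. SAP 12 makes safety descriptive, Protocol 10.1 rests the sample size on no hypothesis, and nothing is decided by these p-values. That stands. A reader might infer that cardiovascular safety is judged by these tests; the documents do not say so.

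A reader might also infer that power is close to zero for every event that matters. That holds only near 0.1% incidence with two- or threefold risks. At 1.0% v 0.5% power is low, not nil, and the documents give no event rates.

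Other replies stand in part.
- SAP 5 reports counts and percentages for categorical data, so incidence will be shown. What is missing is an effect measure with an interval.
- The CVRF item sits in a list of tables presented by treatment arm, so display by dose is a fair reading. Dose is randomised and should not systematically confound CVRF status.
- SAP 12.1 plans TEAEs per treated attack, but by treatment group. It is unclear whether this reaches the CVRF table.
- SAP 4.1 discloses limited subgroup power. It is worded for treatment differences within subgroups, so it does not cover CVRF against no CVRF, nor confounding.
- Nothing in the documents says that CVRF subjects treat more attacks. Step 3 shows what could happen, not what is expected.
- The sentence on confirming safety and efficacy is introductory. Protocol 5.1 to 5.3 state no CVRF objective, so calling this a formal aim would go too far.
- Intervals read only for whether they exclude zero would give the same chance signals, and neither dose stratification nor Bonferroni removes age and sex differences.

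**Conclusion.** The point holds as a defect of analysis and reporting. It does not show that the trial's safety conclusion is unsound. SAP 12.1 plans unadjusted 0.05 tests of every TEAE between non-randomised groups that differ in age and sex by construction, with no interval, exposure handling or pre-listed terms. It is the only hypothesis test in the SAP and the only safety comparison by CVRF: vital signs, ECG, cardiovascular medication changes (12.7) and resource use (13) are not split that way.

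The consequences run in two directions: a false signal among common events is more likely than not across the assumed 20 to 30 terms, and a negative result is close to uninformative for events around 0.1%. These sizes depend on the assumed number of terms, their independence, the CVRF share, the event rates and 2580 as the safety N. Two findings need no assumptions: the reference to Section 11.8 leads nowhere, and Section 11 contains no CVRF analysis. The change should be made.

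**What to change.** - **SAP 12.1, tests.** Replace the 0.05 tests with risk differences and 95% confidence intervals by CVRF status within each randomised dose. Describe them as exploratory and not adjusted for age and sex. Label any p-value that is kept as exploratory.
- **SAP 12.1, exposure.** Add the proportion of treated attacks with a TEAE by CVRF group, with a confidence interval clustered by subject.
- **SAP 12.1, rare events.** Pre-list a set of cardiovascular terms. For subjects with at least one risk factor, give counts and the exact 95% upper bound, once for TEAEs and once for all adverse events after the first dose.
- **SAP 5.1 and 11.1.** Replace the 11.8 reference with a descriptive summary of 2-hour pain-free by CVRF group and dose, placed in 11.1.

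The cost is SAP wording and some extra programming on data already collected. P-values are given up or downgraded. The age and sex differences remain, and the text should say so.

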5. TRIAL OBJECTIVES AND PURPOSE

5.1 Primary objective

To evaluate the safety and tolerability of long-term intermittent use of lasmiditan 100 mg and of lasmiditan 200 mg, as the first and as a second dose, in the acute treatment of migraine.

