10.5.1 Adverse Events

AEs will be coded by the Medical Dictionary for Regulatory Activities (MedDRA) preferred terms, and all summary tables for AEs will be organized by these categories. Frequency counts and percentages will be presented for subjects with AEs within each system organ class and preferred term, separated by treatment arm and dose (the first dose and the second dose for recurrence or rescue or alternative rescue medication). Both subjects ever experiencing an event as well as total events will be presented. Descriptive statistics will also be calculated for each treatment arm and dose (initial and second dose for recurrence or rescue medication) for AE relationship and AE severity. If multiple intensities are reported for a given AE for a subject, the most severe intensity will be counted. A separate, similar analysis will be conducted for TEAEs.

An AE with the date of onset on or within 48 hours after a dose of study drug, or an event that worsens in intensity within 48 hours of a dose of study drug will be considered a TEAE. An AE that occurs in the interval after 48 hours of dosing until the next migraine is dosed will not be considered a TEAE.

SAEs and TEAEs that resulted in termination of the study drug and withdrawal from the study will be presented.

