### **5.4 Analysis of First and Second Doses**

Any analyses based on first dose will only include data observed up to the time of dosing with a second dose. These summaries will be presented based on the first dose taken. The exception to this is the secondary endpoints at the 2-hour time point; if a second dose is taken before the 2-hour time point, the subject will still be included in the summary at 2 hours and will be analysed as having not achieved headache pain-free or MBS-free status at 2 hours.

Any analyses based on the second dose will only include data observed on or after the time of dosing with a second dose. Analyses based on the second dose will be done for both the rescue and recurrence subpopulations.

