### **12.1 Adverse Events**

An AE with the date of onset on or within 48 hours after a dose of study drug, or an event that worsens in intensity within 48 hours of a dose of study drug will be considered a treatment-emergent adverse event (TEAE). Other AEs are defined as those occurring after randomization but not considered to be treatment-emergent.

Descriptive statistics for both number of subjects ever experiencing an event as well as for the total number of events will be presented. Furthermore, descriptive statistics will also be calculated for each treatment group irrespective of first or second dose for AE relationship and AE severity. If multiple intensities are reported for a given AE and subject, then the most severe intensity will be counted. A separate, similar analysis will be conducted for TEAEs.

AEs with a missing start date will be assumed to be treatment-emergent, except in situations described in Appendix 1. If a subject takes at least one dose of study drug, but the date and time of dosing is missing in the e-diary, all AEs for that subject will be considered treatment-emergent, if the AEs occur between available date of dosing as recorded only in CRF for up to 48 hours (2 days) post recorded date of dosing. If the date and time of the second dose is missing in e-diary then all AEs for that subject will be considered as treatment emergent due to second dose, if AEs occur between available date of dosing in CRF for second dose, and an ending boundary of 2 days after recorded date of dosing with second dose, inclusive. See Appendix 1 for derivations related to partial dates and times.

Nausea and/or vomiting reported as adverse events during a migraine by any subject that also noted these as characteristics of their migraine will be presented by treatment groups and not be considered related to treatment but rather an underlying condition of the migraine.

AEs will be coded by the Medical Dictionary for Regulatory Activities (MedDRA) version 21.0.

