Unless otherwise stated, frequencies of adverse events will be displayed by applicable treatment group and overall. AEs will be sorted alphabetically by system organ class (SOC), preferred term (PT), and frequency. For the overall summary of AEs, both total subjects ever experiencing an event as well as total number of events will be presented. For all other summaries, subjects with multiple occurrences of the same AE preferred term will be counted once within the corresponding system organ class and preferred term.

Adverse events will be summarized by treatment arm in the following tables:

- Overall summary of AEs for Safety Population, 6-month, and 12-month population including:
  - All AEs
  - TEAEs
  - Other AEs
  - Related TEAEs
  - AEs leading to study discontinuation
  - Serious AEs
  - Related serious AEs
  - Deaths

- Incidence of All AEs and Other AEs by SOC for the Safety Population and Pre-administrative hold Population.
- Incidence of TEAEs by SOC for the Safety Population, 6 month and 12 month Safety Population.
- Incidence of TEAEs by decreasing frequency of PT for the Safety Population and Pre-administrative hold Population.
- Incidence of TEAEs occurring in more than 2% of subjects by quarter for Safety Population.
- Incidence of TEAEs and SAEs by SOC, PT and Doses for the Safety Population, 6-month and 12-month Safety Population.
- Summary of TEAEs by SOC, PT, and migraine attack sequence for the Safety Population.
- Summary of TEAEs by PT and migraine attack sequence for subjects that treated 5 or more migraine attacks in the Safety Population
- Summary of TEAEs occurring in more than 2% of subjects by PT for the Safety Population.
- Incidence of all SAEs by SOC for the Safety Population, 6 month and 12 month Safety Population.
- Incidence of All AEs leading to study discontinuation for Safety Population, 6-month and 12-month Population.
- Listing of All AEs leading to study discontinuation or death.
- Incidence of serious TEAEs for Safety Population, 6-month and 12-month Population. In addition, listings of these will be presented for Pre-Administrative Hold Population.
- Listing of Serious AEs.
- Time to onset and duration of TEAEs occurring in more than 2% of subjects relative to dosing regardless of second dose. If the time of adverse event is missing, no imputation will be performed for this presentation. The most frequent TEAE list will be finalized before interim soft lock and final database lock.

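### As worded, SAP 12.1 splits adverse events by number of doses taken and specifies no per-attack rate for the second dose, although second-dose safety is part of the primary objective

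*SAP*

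**What the plan says.** Protocol 5.1 sets the primary objective as long-term safety and tolerability "as the first and as a second dose, in the acute treatment of migraine". The primary endpoint in the synopsis is a proportion of patients and a proportion of attacks. Protocol 10.5.1 plans counts and percentages of subjects with adverse events, "separated by treatment arm and dose (the first dose and the second dose for recurrence or rescue or alternative rescue medication".

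SAP 12.1 then gives these rules:

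- Item 2, which builds on the by-subject TEAE table of item 1: "Similar events as Point #1 will be reported when only 1 dose was taken and additionally when 2 doses were taken".
- Item 4, for SAEs: "serious events will be reported when only 1 dose was taken and additionally when 2 doses were taken".
- Item 5, the per-attack TEAE summary: "the adverse events will be reported out of total number of treated migraines for each treatment group regardless of second dose".
- Relationship and severity are described "irrespective of first or second dose for AE relationship and AE severity".
- Time to onset and duration of the common TEAEs are presented "relative to dosing regardless of second dose".

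The table list in the same section includes TEAEs and SAEs broken down by doses, without defining the term. SAP 5.1 removes the second-dose safety population, for a reason that concerns the efficacy populations.

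SAP 5.4 has a time rule: "Any analyses based on the second dose will only include data observed on or after the time of dosing with a second dose". It also stops first-dose analyses at the time of the second dose.

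**The concern.** A second dose comes at least 2 hours after the first. An event that starts in that interval cannot be due to the second dose. A column defined by two doses having been taken still counts it. The column therefore mixes first-dose events with whatever the second dose contributes.

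The by-subject format adds a separate difficulty. Over up to 12 months, the chance that a subject ever has an event in attacks of one kind rises with the number of such attacks. One-dose and two-dose columns can then differ only because the attack counts differ.

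At stake is the second-dose part of the primary objective. A reader of the report would have no specified table giving TEAEs per two-dose attack, or TEAEs with onset after the second dose.

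**Working it through.** The plan has no figure to reproduce: the sample size rests on no hypothesis (Protocol 10.1) and the safety analysis is descriptive (SAP 12). The check is a reading of the text followed by illustrations.

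**1. Unit and rule of each table in SAP 12.1**

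- Items 2 and 4: a by-subject presentation, split by number of doses. Neither the denominator nor the unit (attack or subject) of the split is stated.
- Item 5: all treated attacks as denominator, not split.
- Item 6 (selected attacks in sequence) and item 7 (share of attacks in subjects who had the event): no dose split mentioned.
- Relationship, severity, time to onset: not split.

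If item 2 classifies attacks, events before the second dose are in the two-dose column. If it classifies subjects, events from the one-dose attacks of subjects who ever took a second dose are there as well.

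**2. Carry-over, per attack**

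Let p be the first-dose TEAE risk and q the risk added by the second dose, taken as independent. The two-dose column shows 1 − (1 − p)(1 − q).

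- q = 0: the column shows p in full. With the oral Phase 2 rates in Protocol 4.2, used only as an illustration, that is 73% at 100 mg and 86% at 200 mg, although the second dose adds nothing.
- p = 20%, q = 10% (assumed): 1 − 0.80 × 0.90 = 28%. The first-dose rate is 20/28 = 71% of this.
- p = 73%, q = 5% to 22% (q assumed): 74% to 79%, of which 98% to 93% is the first-dose rate.

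**3. By-subject counts over n attacks, no added risk (q = 0)**

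Incidence = 1 − (1 − p)^n, on the reading that item 2 classifies attacks. The attack counts are assumed.

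| p per attack | 20 one-dose attacks | 2 two-dose attacks |
|---|---|---|
| 5% | 64% | 10% |
| 10% | 88% | 19% |
| 20% | 99% | 36% |

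With 12 attacks of each kind and p = 10%, both columns show 1 − 0.90^12 = 72%. The attack mix alone makes the gap.

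**4. Both effects together**

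Take p = 10% and q = 10% (assumed), so the true per-attack risks are 10% and 1 − 0.90 × 0.90 = 19%.

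- 20 one-dose and 4 two-dose attacks: 1 − 0.90^20 = 88% against 1 − 0.81^4 = 57%.
- 12 and 12: 72% against 1 − 0.81^12 = 92%.

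The same true excess appears as a deficit or as an excess, depending on the mix.

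**5. Windows**

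TEAEs count for 48 h after a dose. With a second dose at t hours (2 to 24), a two-dose attack has a window of 48 + t = 50 to 72 h, or 1.04 to 1.50 times the one-dose window. The two 48 h windows overlap by 48 − t = 46 to 24 h.

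**6. What a split at the second-dose time would achieve**

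Assume exponential onset of first-dose events with median m hours. The share starting before a second dose at t is 1 − 0.5^(t/m). At t = 2 h it is 94%, 75%, 50% and 29% for m = 0.5, 1, 2 and 4 h. At t = 12 h it is at least 87.5% for all four. The split removes much of the carry-over, but not all of it.

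**The case against.** The strongest reply is that the time rule is already in the SAP. Section 5 says that it covers efficacy and safety endpoints alike, and 5.4 speaks of any second-dose analysis. SAP 12.1 also has a rule attributing events to the second dose when its e-diary time is missing, so attribution by time was contemplated. The undefined table by doses could follow the same logic. This stands to the extent that one cannot say the SAP is unable to show second-dose safety, a stronger conclusion that a reader might draw. What remains is that 12.1 nowhere invokes 5.4. Items 2 and 4 are worded by number of doses and lack the rescue and recurrence breakdown that 5.4 requires. The attribution rule covers only missing e-diary times.

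Second, Protocol 10.5.1 itself promises counts of subjects by dose, so a by-subject split is what was planned. That stands: items 2 and 4 should not be deleted. Protocol 10.5 does not expressly promise attack proportions by dose either, so the missing attack-level split is a gap in interpretability rather than a clear breach.

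Third, the mix of 20 and 2 attacks has no source in the documents, and the figures need one of two readings of item 2. That also stands, and the numbers are illustrations only.

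A reader might further infer that two-dose use will look safer than it is. The documents do not support this. Carry-over raises the two-dose column, and a smaller number of two-dose attacks lowers it.

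**Conclusion.** The point holds for the plan as written. Items 2 and 4 split by-subject tables by number of doses, the summary over all treated attacks ignores the second dose, and no table of second-dose TEAEs per attack is specified. SAP 5.4 supplies a better rule, but whether it governs the adverse-event tables is left open.

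The size cannot be fixed from the documents. On assumed inputs the attack mix alone can produce anything from no gap to 88% against 19%, and carry-over alone can put the whole first-dose rate into the two-dose column. When two-dose attacks are the fewer, these effects oppose each other, so the net direction is unknown. The illustrations rest on constant per-attack risk, independence between attacks and doses, and assumed attack counts and added risks.

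The second-dose part of the objective is thus addressed by tables that are hard to interpret; it is not left without data. Start times of adverse events are collected (Protocol 9.2.1) and the e-diary records dose times (SAP 5), so the gap lies in the specification.

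**What to change.** In SAP 12.1, keep items 1 to 5 and add:

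1. A statement that the SAP 5.4 time rule governs the dose split of adverse events, including the table by doses.
2. Definitions of the unit and denominator for items 2 and 4 and for that table.
3. Attack-level TEAE and SAE tables by arm:
   - one-dose attacks: events per one-dose attack;
   - two-dose attacks, onset before the second dose: assigned to the first dose;
   - two-dose attacks, onset from the second dose to 48 h after it: two-dose attacks as denominator, shown by rescue and recurrence.
4. A separate row for two-dose attacks with no e-diary second-dose time. These should not be assigned by CRF date in the new tables: SAP 5 says that CRF dosing times are unavailable, so a date rule would bring same-day events from before the second dose back into the second-dose count.

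The cost is SAP wording and modest extra programming on data already collected, plus a time-unknown row to explain. The result stays descriptive: the 48 h windows overlap, and taking a second dose is not randomized. The tables would show events after the second dose without isolating its causal contribution.
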